6.9 Assessment and management of risk

Benefits – the anticipated benefits of the intervention are an improvement in health related quality of life, and a reduction in symptom burden. The risk of harm with exercise based interventions is very low. The risk of an adverse event with an exercise intervention is highest in those with pre-existing cardio-vascular disease.

These complication rates are low, it should be noted that patients were screened and exercised in medically supervised settings equipped to handle cardiac emergencies.

Staff will be trained to deliver exercise interventions to individuals with multiple long term conditions and adapt the training programme as necessary, taking into account individuals baseline exercise capacity, symptoms and response to the exercise programme. The progression of exercise will be reviewed weekly and progressed as appropriate.

There is no anticipated risk to the research team.

If the participants have any concerns about the delivery of care they will be directed towards the Patient Advice and Liaison Service within the respective trusts where the intervention is to be delivered.

The investigator may discontinue a participant from the study at any time if the investigator considers it necessary for any reason including if the participant loses mental capacity.

6.10 COVID Pandemic Adaptations

In the event of a pandemic we will operate the following regimes with full advice and approvals from infection control leads at the participating sites. All infection control measures will be instigated. All programmes will run with 'social distancing' of participants. All cleaning procedures will be followed. There is national guidance for pulmonary rehabilitation developed by the British Thoracic Society and this will be used as a reference document for our programme. In the event of a lockdown we have contingency funding to develop of a digital programme. This will be developed by a Leicester software company (HARK2) who have worked with the team previously to develop a bespoke respiratory and cardiac website to support a remotely delivered rehabilitation programme.

6.11 End of trial

This study will end when the specified number of participants have been recruited, all participants have completed their last follow up visit, data validation has taken place and the database is locked and statistical analysis complete.

6.12 Storage and analysis of clinical samples

There will be no blood or tissue samples collected.

6.13 Recording and reporting of SAEs Definitions

| Term | Definition |
|------|------------|
| | |

Adverse Event (AE)

Any untoward medical occurrence in a patient or clinical investigation participants, which does not necessarily have to have a causal relationship with this treatment.

An AE can therefore be any unfavourable and unintended sign (including an abnormal laboratory finding), symptom or disease temporally associated with the the study, whether or not considered related to the study.

For this study, only those deemed related to the PERFORM rehabilitation programme (intervention) or study assessments will be documented on an AE log and in the patient's medical notes.

Adverse Reaction (AR)

An untoward and unintended response in a participant to an investigational medicinal product which is related to any dose administered to that participant.

The phrase "response to an investigational medicinal product" means that a causal relationship between a trial medication and an AE is at least a reasonable possibility, i.e. the relationship cannot be ruled out.

All cases judged by either the reporting medically qualified professional or the Sponsor as having a reasonable suspected causal relationship to the trial medication qualify as adverse reactions. It is important to note that this is entirely separate to the known side effects listed in the SmPC. It is specifically a temporal relationship between taking the drug, the half-life, and the time of the event or any valid alternative etiology that would explain the event.

For this study, only those deemed related to the PERFORM rehabilitation programme (intervention) or study assessments will be documented on an AE log and in the patient's medical notes

Serious Adverse Event (SAE)

A serious adverse event is any untoward medical occurrence

- results in death
- is life-threatening
- requires inpatient hospitalisation or prolongation of existing hospitalisation
- results in persistent or significant disability/incapacity
- consists of a congenital anomaly or birth defect

Other 'important medical events' may also be considered serious if they jeopardise the participant or require an intervention to prevent one of the above consequences.

NOTE: The term "life-threatening" in the definition of "serious" refers to an event in which the participant was at risk of death at the time of the event; it does not refer to an event which hypothetically might have caused death if it were more severe.

For this study, only SAEs deemed related to the PERFORM rehabilitation programme (intervention) or study assessments

| Version 2.0 10.IVIA1.2025 | will be reported and reviewed by the PSC and Sponsor. SAEs will be reviewed by the site PI to determine relatedness. |
|---|--|
| Serious Adverse Reaction (SAR) | An adverse event that is both serious and, in the opinion of the reporting Investigator, believed with reasonable probability to be due to one of the trial treatments, based on the information provided. |
| | For this study, only SAEs deemed related to the PERFORM rehabilitation programme (intervention) or study assessments will be reported and reviewed by the PSC and Sponsor. SAEs will be reviewed by the site PI to determine relatedness. |
| Expected Serious Adverse Events/Reactions | Only related SAE/SARs will be reported for the PERFORM feasibility study due to the nature of the patient population and feasibility aspect of this study. There are no expected serious adverse events/reactions, however due to the exercise nature of the PERFORM rehabilitation programme and assessments, injuries such as musculoskeletal injuries, etc. may be deemed related and 'expected' as such. These will be evaluated on a case-by-case scenario and will be decided by PI and/or CI. |
| Suspected Unexpected Serious Adverse Reaction | A serious adverse reaction, the nature and severity of which is not consistent with the information about the medicinal product in question set out in the reference safety information: |
| (SUSAR) | in the case of a product with a marketing authorisation, this could be in the summary of product characteristics (SmPC) for that product, so long as it is being used within it's licence. If it is being used off label an assessment of the SmPCs suitability will need to be undertaken. in the case of any other investigational medicinal product, in the investigator's brochure (IB) relating to the trial in question |

NB: to avoid confusion or misunderstanding of the difference between the terms "serious" and "severe", the following note of clarification is provided: "Severe" is often used to describe intensity of a specific event, which may be of relatively minor medical significance. "Seriousness" is the regulatory definition supplied above.

Detailed guidance can be found here:

http://ec.europa.eu/health/files/eudralex/vol-10/2011 c172 01/2011 c172 01 en.pdf

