A Programme Steering Committee (PSC) has been established to provide independent expert oversight of the PERFORM research programme and includes Trial Steering Committee (TSC) and Data Safety and Monitoring Committee (DSMC) responsibilities for WPs 3-5 (feasibility study and main trial). PSC meetings will normally take place once a year to provide overall supervision of the trial and ensure that the trial is conducted to the rigorous standards set out in the guidelines for good clinical practice; however the PSC may be convened during the recruitment phase of WP3 to advise/address any WP3 study concerns. The PSC consists of an independent chair, an independent statistician, other independent members who are experts in rehabilitation and multimorbidity, two patient representatives, meetings may also be attended by with PERFORM co-chief investigators, study manager, the sponsoring organisation, and representatives from the clinical research networks. The PSC will consider progression to full trial (WP4) following completion of the feasibility study (WP3). The PSC will make recommendations to the PMG and will report to the sponsor and the funder.

The routine reports reviewed by the PSC will include a summary of all SAEs. SAEs identified as related, life-threatening or resulting in death will be reported annually to the PSC members for review, unless requested more frequently by PSC. The decision regarding frequency of review may be re-evaluated by the PSC members throughout the study delivery, and then reported to the Sponsor for continuity in safety reporting.

TRIAL FLOW CHART

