6.13.1 Reporting Procedures for Serious Adverse Events

All SAEs related to the PERFORM study or rehabilitation programme (intervention) occurring from the time of written informed consent until the 3 month follow up visit must be reported to the Sponsor immediately and within 24 hours of becoming aware of the event. These related SAEs will be reported using appropriate forms and according to the Sponsor SOP for reporting serious adverse events. Additional information will be provided if requested to the Sponsor and main Research Ethics Committee (REC). The Principal Investigator or another delegated physician (as agreed by the Sponsor) is responsible for

the review and sign off of the SAE and the assessment of causality (i.e. whether an event is related to a study procedure or intervention).

If a delegated clinican from the reporting site is unavailable at the time of identification of a SAE the initial report without assessment of whether the event was related to the study or intervention should be submitted to the Sponsor. This must be completed immediately and within 24 hours of the study team becoming aware of the SAE, and must be followed-up by medical assessment as soon as possible thereafter.

The Sponsor will perform an initial check of the information and ensure that the SAE line listing is reviewed by the Director of Research & Innovation. All SAE information must be recorded on an SAE form and sent to the Sponsor. Additional information received for a case (follow-up or corrections to the original case) needs to be detailed on a new SAE form and sent to the Sponsor.

Copies of all documentation and correspondence relating to SAEs will be stored in the TMF and / or ISF

For each SAE the following information will be collected:

- a) full details in medical terms and case description
- b) event duration (start and end dates, if applicable)
- c) action taken
- d) outcome
- e) seriousness criteria
- f) relationship to the study procedure or intervention

Any change of condition or other follow-up information should be emailed to the Sponsor as soon as it is available or at least within 24 hours of the information becoming available. Events will be followed up until the event has resolved or a final outcome has been reached."

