10.6 Participant population

The analysis of the feasibility outcomes will be carried out in the ITT population.

Patient reported outcomes and clinical events will be analysed using the complete case population for the variable being summarised.

Adverse events will be analysed in the safety population, that all individual randomised with individuals receiving one or more session of the PERFORM intervention being analysed in the PERFORM intervention arm.

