10.7 Procedure(s) to account for missing or spurious data

Feasibility outcomes: For the feasibility outcomes relating to completeness of data there will be no need to account for missing data as this is exactly what the data is measuring fully completed or not (missing). Likewise, the number randomised will not need to account for missing data. For the proportion of sessions by patients in the PERFORM intervention arm, if the data for attendance at any session is truly missing and can be dissolved through data queries, individuals will be assumed to have not attend that session.

Patient outcomes/clinical events: sites will be asked to check completion of patient outcomes in order to mimimise any missing data. If items are missing from within an outcome questionnaire, the appropriate imputation method will be applied to allow outcome scoring. Data presentation for this feasibility study will consider completed outcomes and not impute any complete missing outcomes.

10.8 Other statistical considerations.

A statistical analysis plan will be finalised prior to final data lock and any deviations from the statistical plan will be reported in the statistical report.

[figure not shown]
Separate listings of SAEs will be presented as line listings; in addition to the description listing will include relatedness to intervention.

The number of serious adverse events will be presented overall and by randomised group. The number of patients with 0, 1, 2 etc events will be summarised overall and by randomised group.

The type and number (percentage) of protocol deviations will also be tabulated overall and by randomised group in the ITT population.

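### The protocol routes SAEs to the oversight committee in two incompatible ways, and its related-only rule leaves the by-arm SAE counts not comparable

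*Protocol*

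**What the plan says.** Four parts of the protocol bear on this point.

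- **Section 6.13 (definitions table).** The SAE and SAR entries both say that "only SAEs deemed related to the PERFORM rehabilitation programme (intervention) or study assessments will be reported and reviewed by the PSC and Sponsor". The entry on expected events repeats the rule and gives a reason: "Only related SAE/SARs will be reported for the PERFORM feasibility study due to the nature of the patient population and feasibility aspect of this study". On who decides: "SAEs will be reviewed by the site PI to determine relatedness".
- **Section 6.13.1.** The 24-hour route to the Sponsor covers related SAEs from consent to the 3-month visit: "These related SAEs will be reported using appropriate forms and according to the Sponsor SOP for reporting serious adverse events". The section also allows a delegated physician to judge causality and lets a report go in unassessed if no clinician is available. A later sentence, not limited to related events, asks for SAE information to go to the Sponsor on a form.
- **Roles and responsibilities, PSC.** This committee carries the steering and data-monitoring duties for work packages 3 to 5, and the feasibility study is named among them. "The routine reports reviewed by the PSC will include a summary of all SAEs". In addition, "SAEs identified as related, life-threatening or resulting in death will be reported annually to the PSC members for review", unless the committee asks for more frequent review.
- **Sections 10.6 and 10.8.** Section 10.8 plans that "The number of serious adverse events will be presented overall and by randomised group", with a count of patients by number of events and a line listing that shows relatedness to the intervention. Section 10.6 defines a safety population of all randomised patients, with "individuals receiving one or more session of the PERFORM intervention being analysed in the PERFORM intervention arm".

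**The concern.** There are two linked problems. First, the body with data-monitoring responsibility has its SAE feed defined in two ways, and a site or trial office cannot comply with both. This cannot be left to the statistical analysis plan, because an SAE that is never reported cannot be analysed later.

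Second, the by-arm SAE table depends on a filter that is itself tied to the arm. A hospital admission that counts as an SAE in a PERFORM patient, because it is thought to follow from exercise, has no equivalent route into the table for a usual-care patient. A reader who takes the two columns at face value, including those planning the full trial, would be comparing events selected in different ways.

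**Working it through.** **Step 1: the two routing rules side by side.** There is no stated figure to reproduce, so the check is textual.

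| Event | Section 6.13 | PSC section |
|---|---|---|
| SAE judged related | Goes to PSC | Goes to PSC |
| Fatal or life-threatening SAE judged unrelated | Does not go | Goes, in the summary and for annual review |
| Other SAE judged unrelated | Does not go | Goes, in the summary |

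The rules agree only in the first row. One might read the PSC summary as covering all *reported* SAEs. That would leave the words on life-threatening and fatal events with no work to do, since a related-only feed already contains every such event that is related. They make sense only if unrelated events also arrive.

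**Step 2: what can enter the by-arm table.** Under section 7.2 control patients have usual care alone, so their SAEs qualify only through study assessments. Under section 7.1 PERFORM patients also have an 8-week supervised programme, so their SAEs qualify through assessments or the programme. The filter differs by arm whatever the true risks are.

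**Step 3: size, as an illustration.** From section 10.1, n = 40 PERFORM and 20 control (60 at 2:1). The protocol gives no SAE risk and no share judged related, so these are assumptions: the same all-cause 3-month risk r in both arms (5%, 10%, 20%), a share s = 25% judged related in PERFORM, and a share c = 0–5% judged assessment-related in control. Expected events are n × r; expected events shown are n × r × s or n × r × c. The chance that the control column is empty is (1 − r × c)^20, taking at most one event per patient.

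| r | All SAEs, PERFORM v control | Shown, PERFORM | Shown, control | Chance control column is zero |
|---|---|---|---|---|
| 5% | 40×0.05 = 2 v 20×0.05 = 1 | 2×0.25 = 0.5 | 0 to 1×0.05 = 0.05 | 95.1–100% |
| 10% | 4 v 2 | 4×0.25 = 1 | 0 to 2×0.05 = 0.1 | 90.5–100% |
| 20% | 8 v 4 | 8×0.25 = 2 | 0 to 4×0.05 = 0.2 | 81.8–100% |

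With s = 10% the PERFORM figures fall to 0.2, 0.4 and 0.8. Direction can also be lost: if PERFORM truly halved risk (10% v 20%), s = 25% and c = 5% would show 0.10×0.25 = 2.5% v 0.20×0.05 = 1.0%.

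**Step 4: grouping.** Section 10.6 places anyone with at least one session in the PERFORM arm for adverse events. Section 10.8 presents SAEs by randomised group. The two differ for any control patient who attends a session.

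**The case against.** The best case for the plan has several parts.

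*Related-only reporting is deliberate.* It is stated for this study, with a reason, in a population in which many unrelated events are likely. The PSC text describes a programme-wide committee, so the specific rule could be read as overriding the general one. The choice to expedite only related events is legitimate and need not change. The override reading does not resolve the conflict, because the PSC text names the feasibility study and sits in this protocol.

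*All-cause data exist.* Sections 2.4.1 and 10.2.3 collect deaths and hospital admissions in both arms, without a relatedness filter, and summarise them by randomised group. This stands as a real mitigant. It covers two of the seriousness criteria, is a 3-month complete-case summary, and has no stated route to the PSC or the SAE tables.

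*Nothing formal rests on the table.* The SAE output is descriptive, section 10.2.3 rules out P-values, and no progression criterion in section 2.2 uses SAEs. This also stands, and it limits the severity.

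A reader might infer more than the text supports:

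- That the control count is zero by definition. It is restricted, not zero: controls do the same physical assessments, including the shuttle walk.
- That the table must make PERFORM look worse. Both columns can be empty: at r = 10% and s = 25% the PERFORM column is empty with chance (1 − 0.025)^40, about 36%.
- That an excess of harm could never be seen. The deaths and admissions data contradict this.
- That the relatedness column would be constant. It concerns the intervention, so assessment-related or not-yet-assessed SAEs could differ.
- That the person judging relatedness is unblinded. The protocol does not say so.
- That PERFORM patients with no session leave that arm in the safety set. Section 10.6 does not say so.

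**Conclusion.** The point holds on two counts. The PSC section and section 6.13 give incompatible rules for which SAEs reach the committee with data-monitoring duties, and a death judged unrelated is the clearest case. The SAE counts by randomised group in section 10.8 would be selected differently by arm and are not comparable. Both follow from the text and need no assumed rate.

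The size is illustrative only: under equal true risks of 5% to 20%, expected counts of 2 v 1 to 8 v 4 would appear as about 0.5 v 0–0.05 to 2 v 0–0.2, given the assumed shares judged related. The mismatch in grouping between sections 10.6 and 10.8 is a smaller matter that also needs one answer.

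This should be fixed. With descriptive tables, no progression rule that uses SAEs, and all-cause deaths and admissions in both arms, it does not threaten the study's main conclusions.

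**What to change.** - Record all SAEs in both arms on the CRF from consent to the 3-month visit, with a relatedness field that separates intervention from study assessments. Leave the existing 24-hour reporting route for related SAEs unchanged.
- Reconcile the PSC section with sections 6.13, 6.13.1 and 10.8, so that one rule says what the committee receives and what the Sponsor receives.
- In section 10.8, tabulate all-cause SAEs by randomised group and give related events as a separate row.
- State one grouping for the SAE tables, so that sections 10.6 and 10.8 agree.

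If the sponsor prefers to keep related-only recording, the minimum is to limit the PSC section and section 10.8 to related SAEs and label the table as not comparable between arms.

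The cost is a protocol amendment and a small amount of extra site data entry. Deaths and hospital admissions are already being collected as clinical events.

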The Sponsor will report all SUSARs to the Research Ethics Committee concerned. Fatal or life-threatening SUSARs must be reported within 7 days and all other SUSARs within 15 days. The CI will inform all investigators concerned of relevant information about SUSARs that could adversely affect the safety of participants.

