7. INTERVENTION & CONTROL

7.1 Intervention group

The PERFORM rehabilitation programme will comprise an 8 week supervised rehabilitation programme, 6 weeks, twice weekly then 2 weeks, once a week that will be offered in either a primary or secondary care setting. Each session will last for 2 hours (1hr of 'move and improve

exercise sessions, and 1hr patient 'Health and Wellbeing' self care support session and Q&A/opportunity to interact with the group). The intervention will be offered within 4 weeks of randomisation.

The rehabilitation programme will comprise an exercise component with an accompanying education programme. The 'Health and Wellbeing' self care support sessions / educational package will offer advice and support for behaviour change to support positive lifestyle changes and symptom management. Much of the advice will be appropriate to all participants for example health eating, the benefits of exercise, stress management and relaxation techniques, medicines adherence, and exacerbation of symptoms. The aim of the education 'health and wellbeing' package is to support symptom management, risk factor management and enhance self-management skills. The education programme will be delivered by healthcare professionals delivered as informal and interactive sessions. The information will be supplemented by written leaflets and material to support the individual to share with their family and carers. After the 8 week programme the participant will have a discharge appointment in most cases this will take place 1-2 weeks following the last rehabilitation session.

Each 'move and improve' exercise session will offer an individually prescribed and progressed aerobic walking programme (a combination of walking (treadmill where available). In addition resistance training will be delivered that will be individually prescribed and progressed.

Participants will also be encouraged to complete a home exercise programme that will be closely monitored. A home exercise booklet will be provided as well as a progress tracker standardised exercise diary that will ask participants to record exercise frequency, duration and symptom scores post bout of exercise. This will be recorded for the aerobic and resistance programme.

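### The only event-triggered expedited report to the ethics committee depends on a SUSAR definition written for medicinal products, which this exercise trial cannot meet as worded, and expectedness has no fixed reference

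*Protocol*

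**What the plan says.** The definitions table in Protocol section 6.13 describes a SUSAR as "A serious adverse reaction, the nature and severity of which is not consistent with the information about the medicinal product in question". It gives two possible references: "in the case of a product with a marketing authorisation, this could be in the summary of product characteristics (SmPC) for that product", and "in the case of any other investigational medicinal product, in the investigator's brochure (IB) relating to the trial in question". Section 6.13.1 then states that "The Sponsor will report all SUSARs to the Research Ethics Committee concerned". Fatal or life-threatening SUSARs are due within 7 days and others within 15. The Chief Investigator (CI) must tell the other investigators of relevant safety information, again about SUSARs.

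On expectedness, section 6.13 states: "There are no expected serious adverse events/reactions". The same sentence goes on to allow that musculoskeletal and similar injuries may be deemed expected, and the next adds: "These will be evaluated on a case-by-case scenario and will be decided by PI and/or CI".

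Section 7.1 describes what is being tested: "The rehabilitation programme will comprise an exercise component with an accompanying education programme". No medicinal product is under study.

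**The concern.** A reporting clock runs only if the event that starts it can be recognised. Here that event is defined by inconsistency with product information, and there is no product. Suppose a participant has a serious cardiac event during a supervised session and the site Principal Investigator (PI) judges it related. The Sponsor hears within 24 hours. Taken at its word, the protocol then requires no timed report of that event to the REC and no notice to the other sites running the same sessions, unless an urgent safety measure is also taken.

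The case is foreseeable. Section 6.9 says the risk of an adverse event with exercise is highest in people with existing cardiovascular disease, and section 5.1 admits people with coronary heart disease and heart failure. Participant protection and cross-site awareness are at stake. No estimate or analysis is affected.

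**Working it through.** No arithmetic applies. The check sets the definitions beside the reporting routes.

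1. **Can the SUSAR definition be met?** It needs a reference against which an event is inconsistent. The two references named are a summary of product characteristics and an investigator's brochure, both tied to a medicinal product. Section 7.1 describes exercise and education. The reference cannot exist, so the condition cannot be satisfied as worded.

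2. **Is the drug wording adapted elsewhere in the table?** The adverse event, adverse reaction, SAE and serious adverse reaction entries each carry a study-specific sentence pointing to the PERFORM programme. The adverse reaction entry opens with the same borrowed wording ("An untoward and unintended response in a participant to an investigational medicinal product") but is then adapted. The SUSAR entry has no such sentence.

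3. **What depends on the term?** The routes in the protocol are:
   - Related SAE to Sponsor: 24 hours (6.13.1). No product condition, so it works.
   - Related SAE to the Programme Steering Committee (PSC), which holds the data monitoring role: annually unless the PSC asks for more (roles and responsibilities section; also 6.13). It works, but it is not expedited by default.
   - SAE information to the REC: further information on request, with no time limit (6.13.1).
   - SUSAR to REC: 7 or 15 days (6.13.1). Blocked by step 1.
   - CI's notice to other investigators: SUSARs only (6.13.1). Blocked by step 1.
   - Urgent safety measure to Sponsor and REC: at once, and within 3 days at most (6.14). Triggered by a measure being taken, not by the event, and it does not name the other sites.
   - Annual progress report to the REC (13.4). Not expedited.

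   The SUSAR is therefore the only event that starts a timed REC report, and the only trigger for alerting other investigators.

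4. **Would replacing the product with the programme be enough?** Not quite. A SUSAR must first be a serious adverse reaction, whose core definition refers to trial treatments. Reportable SAEs also include those caused by study assessments, such as the incremental shuttle walk test (6.8.1), which both arms perform. An assessment is not a treatment, so the trigger has to name both.

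5. **Is there a standard for expectedness?** The protocol sets a default of none expected, then an open-ended exception for injuries decided individually by the PI and/or CI. No list is fixed in advance. Items a to f collected for each SAE in section 6.13.1 end with relationship and do not include expectedness, so the specified items hold no record of the judgement.

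**The case against.** The strongest reply is that this is a drafting remnant and that a sensible Sponsor would read the sections together, treating any related SAE not deemed expected as reportable. The serious adverse reaction entry speaks of trial treatments, not drugs, and the none-expected statement can be read as a default with an exception. Section 6.13.1 also refers to a Sponsor procedure for SAE reporting that is not shown. This carries weight: the documents show a defective trigger, not that any event would go unreported. It does not remove the fault, because a protocol should not rely on staff setting aside its own definition.

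A reader might infer more than the text supports in four ways:

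- **That the SUSAR is the only expedited route to the REC.** It is not. Section 6.14 gives a faster one, although it needs a measure to have been taken.
- **That case-by-case expectedness itself blocks the report.** It does not, since an event can still be judged unexpected. The block comes from the product wording alone.
- **That injuries can be reclassified once their outcome is known.** The protocol says nothing about timing relative to outcome, and any judgement about a particular event follows its occurrence. The sound point is the missing reference list. The exception is also framed around exercise-type injuries, and a cardiac arrest is not naturally one of them.
- **That participants are left unprotected.** The 24-hour Sponsor report, the Sponsor's review of the SAE line listing, the PSC's review and the monitoring of SAEs throughout the study (10.5) all continue, whether or not an event is called expected.

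**Conclusion.** The point holds in a limited form. As worded, no related and unexpected SAE meets the SUSAR definition, so the 7-day and 15-day REC reports and the CI's notice to investigators have no workable trigger. This is a literal reading of the text, not an estimated rate of missed reports. It assumes that the unseen Sponsor procedure does not supply a different definition. If it does, the practical gap is smaller, but the protocol still needs to agree with it.

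Expectedness is a second, lesser fault. It is stated inconsistently, has no fixed reference and is absent from the listed SAE items. Both faults should be corrected because the change is cheap and bears on participant safety.

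**What to change.** In section 6.13, replace the SUSAR definition with a related and unexpected SAE: one judged related to the PERFORM programme or to a study assessment, and not on a list of expected serious events fixed in the protocol before the first participant. The list may be empty. Use the same term as the trigger in section 6.13.1, keeping the stated 7-day and 15-day clocks and the CI's duty to inform investigators.

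Reconcile the two expectedness statements in section 6.13 with that list, and add expectedness to SAE items a to f in section 6.13.1. The adverse reaction entry can stay, since it triggers no REC report and already carries a study-specific adaptation.

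The cost is a protocol wording amendment with a matching change to the SAE form, and possibly a few more REC reports.
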